4.7 Accountability/Receipt/Storage and Handling of IMP

The Investigator, or a delegated individual (e.g. pharmacist), must ensure that the study drug is stored and dispensed in accordance with hospital standard operating procedures and applicable regulatory requirements. The medication provided for this study is for use only as directed in the protocol.

Drug dispensing and accountability logs will be provided to the sites in a Pharmacy Site File and a system will be established to ensure that:

- Deliveries of investigational products from Bayer Healthcare and Merck Serono GmbH are received by a responsible person at the distributing pharmaceutical lab e.g. pharmacist or suitable pharmacy designee, and are handled and stored correctly
- Distribution of investigational products to participating centres is managed by a responsible person e.g. pharmacist or suitable pharmacy designee
- Deliveries of investigational products from the distributor are received by a responsible person e.g. pharmacist or suitable pharmacy designee, and are correctly handled and securely stored.
- Investigational products are dispensed in accordance with the protocol, local dispensing policies, and normal excursion management practices. Ideally, investigational products will be dispensed

directly to study participants. However, if the local dispensing policy permits the LCO to collect the study IMP from pharmacy on behalf of the participant, all procedures documented in the latest version of the PROVENT IMP/Pharmacy Manual, must be adhered to, e.g. a review of the chain of custody stages, use of a 'Chain of Custody' Log

- Participants return any unused investigational product and empty containers to the Research Team for return to pharmacy
- A Dispensing Log is accurately maintained. This will include the initials and study number of the
 participant to whom the investigational product was dispensed, the pack number from the outer
 carton, the date of dispensing and the date any unused investigational product is returned to the
 pharmacy. Any discrepancies must be accounted for on the Dispensing Log. This record is in
 addition to any drug accountability information recorded in the CRF.
- On completion of each patient's treatment, the Dispensing Log will be returned to the coordinating centre or collected at a monitoring visit, and a copy retained in the PROVENT pharmacy file.

The patients will return unused tablets and bottles of oil every six months, and these will be returned to the pharmacy for reconciliation and disposal or destruction locally as agreed. Details of the remaining quantities of drugs will be collected by a member of the research team at regular intervals so that these may be recorded on the CRF. A Drug Destruction Form will be completed by the pharmacist or suitable designee and filed in the PROVENT pharmacy site file.

Certificates of delivery or return, and destruction, must be signed by a pharmacist or suitable pharmacy designee and copies retained in the Pharmacy Site File.

4.8 Dispensing of IMP

Participating pharmacies will dispense a six months' supply of IMP to the participant on receipt of the study specific prescription form. The patient's details and pack code will be recorded on the PROVENT Dispensing Log and the detachable label from the container attached to the Log. The medication dispensed will contain the correct amount of IMP required to complete 6 months of treatment, plus an additional 4 weeks to allow for two delayed appointments of up to two weeks.

Participants will be asked to record the date of any missed dose on the diary card provided to them every 3 months. Should a participant damage or mislay his medication, he should contact the local co-ordinator or a member of the research team, who will liaise with the PROVENT Coordinating Centre and arrange for replacements to be delivered to the pharmacy. Once the patient has collected the medication, the details should be documented on the PROVENT Dispensing Log.

Local dispensing guidelines will be followed, and each staff member who dispenses the IMP will sign the PROVENT Dispensing Log to document appropriate IMP tracking. Trial initiation and set-up will be carried out by the central co-ordinating team, and members of the trial team at participating pharmacies should ensure that they have had study specific training and their involvement documented on the PROVENT trial delegation log.

4.9 IMP Stability

The Vitamin D3 and matched placebo should be stored below 25°C and protected from light. It should not be used after the expiry date stated on the packaging.

The aspirin and matched placebo should be stored below 25°C in a dry environment. Excursions outside this normal range may be tolerated for short periods. It should not be used after the expiry date stated on the packaging

IMPs should be stored in the numbered packs in which they are supplied, and the individual components not separated. Pharmacies will be responsible for dispensing in line with their local dispensing procedures and normal excursion management practices. If the IMP does experience an excursion outside the ranges stipulated by the manufacturer, guidance will be sought from that manufacturer.

4.10 Prior and Concomitant Therapies

Concomitant medicines will be recorded at baseline and at all subsequent visits. The case report forms will document details of all current prescription or self-medication, and any used in the previous six months.

Participants should not currently be taking any concomitant aspirin, aspirin containing products or NSAIDs, or have taken these regularly (daily for 6 months or more) within two years of randomisation. Vitamin D3 supplements containing greater than 400IU (10micrograms) per day, or replacement Vitamin D3 medication prescribed by a physician, should not have been taken regularly (daily for 6 months or more) within two years of randomisation.

Individuals should not be taking any other investigational agents/drugs, nor any of the following medication:

Potential Aspirin Interactions:

Enhanced effects ranging up to an increased risk of side effects:

- Anticoagulants / Thrombolytics: Acetylsalicylic acid can increase the risk of bleeding when taken before thrombolytic treatment. Attention should therefore be paid for signs of external or internal bleeding (e.g. bruising) in patients who are scheduled to undergo thrombolytic treatment.
- Antiplatelet drugs, e.g. ticlopidine, clopidogrel: the bleeding time can be prolonged.
- Other non-steroidal anti-inflammatory drugs and anti-rheumatics in general: risk for gastrointestinal bleedings and ulcers are increased.
- Systemic glucocorticoids (with the exception of hydrocortisone as replacement therapy for Addison's disease): increased risk for gastrointestinal side effects.
- Alcohol: elevated risk of gastrointestinal ulcers and bleeding with excessive intake.
- Digoxin: elevated plasma level
- Antidiabetics: the blood glucose level can be reduced.
- Methotrexate: decrease in elimination and displacement from protein binding sites by salicylates.
- Valproic acid: displacement from protein binding sites by salicylates.
- Selective-Serotonin-Re-uptake Inhibitors (SSRIs): elevated risk of gastrointestinal bleeding due to synergistic effects.

Weakening of effects:

- Aldosterone antagonists (spironolactone and canrenoate);
- Loop diuretics (e.g. furosemide);
- Antihypertensives (especially ACE inhibitors);
- Uricosuric agents (e.g. probenecid, sulphinpyrazone).

Experimental data suggest that ibuprofen may inhibit the effect of low dose acetylsalicylic acid on platelet aggregation when they are dosed concomitantly. However, the limitations of these data and the uncertainties regarding extrapolation of ex vivo data to clinical SPC/low dose aspirin situation imply that no firm conclusion can be made for regular ibuprofen use, and no clinically relevant effect is considered to be likely for occasional ibuprofen use.

Accordingly, patients should not take aspirin in conjunction with any of the above-mentioned substances unless expressly instructed to do so by a doctor.

Potential Vitamin D3 drug interactions:

- Phenytoin or barbiturates: Plasma concentrations of 25-OH D may be decreased and metabolism to inactive metabolites may be increased.
- Thiazide diuretics can lead to hypercalcaemia due to reduced calcium excretion via the kidneys. Therefore, plasma and urinary calcium levels should be monitored during long-term treatment.
- Glucocorticoids: Simultaneous administration can impair the effect of Vitamin D3.
- Digitalis (cardiac glycosides): Oral administration of Vitamin D3 may increase the efficacy and the toxicity of digitalis due to increased calcium levels (risk of cardiac arrhythmias). The ECG as well as plasma and urinary calcium levels and possibly also digoxin and digitoxin plasma levels should be monitored in such patients.
- Vitamin D3 metabolites or analogues (e.g. calcitriol): It is recommended to combine with Vigantol Oil only in exceptional cases and with monitoring of serum calcium levels.
- Rifampicin and isoniazid: May increase the metabolism of Vitamin D3 and reduce its effectiveness.
- Dovonex cream (calcipotriene) may increase serum calcium levels

The following drugs should be used with caution due to the potential decrease in efficacy that may occur with high doses of vitamin D3

- Calcium channel blockers (verapamil, diltiazem, nifedipine, nicardipine): Vitamin D3 in large doses may decrease the efficacy of these drugs
- Statins (atorvastatin and lovastatin): efficacy may be reduced with Vitamin D3.

Patients must be instructed not to take any medications, including all over the counter products such as vitamins, minerals, and other dietary supplements, without first consulting with the investigator.

The concurrent administration of other anticancer therapy, including cytotoxic, hormonal or immunotherapy are prohibited during the study treatment phase.

4.11 Dose modification/reduction/delay

Administration of the Vitamin D3/placebo may be delayed if a participant experiences symptoms of hypercalcaemia.

Dyspepsia has been shown to be a risk factor for NSAID GI bleeding [46]. Therefore, should new dyspeptic symptoms arise, or a gastrointestinal bleed occur (melaena, haematemesis, decreased haemoglobin) during the course of the study, then treatment with aspirin/aspirin placebo should cease immediately and permanently, and the patient will withdraw from the study.

Helicobacter pylori (H. pylori) has also been shown to be a causative factor in GI bleeding, and all participants will undergo a detection test for this at randomisation as a precaution. Patients will be allowed to start their study medication, including aspirin/placebo aspirin, prior to obtaining the result of this test, as patients are not normally tested for this infection before commencing aspirin therapy and the maximum aspirin dose in this study is very low. If the test result is positive, the patient will be required to take a course of proton pump inhibitors (PPIs) and antibiotics if they wish to continue on the study, to reduce any additional risk of gastric bleeding. In all cases, the GP will be informed of the result of the test, and if positive, the patient will also be sent a copy of the GP letter and asked to see his GP to complete a course of treatment. They will not need to stop the study medication, but may not continue on the study without completing the H Pylori treatment. Once treated, there is no requirement to retest for this infection (as per NICE guidelines).

As a precautionary measure, the aspirin/placebo tablets should be stopped 7 days prior to prostate biopsy, or any other planned surgery [47, 48]. These may be restarted if there are no signs of significant bleeding 48 hours after the procedure, or at the discretion of the treating clinician. Patients will be reminded about this in the clinic, and information is also included in the PIS and Diary Cards. There is no need to stop the Vitamin D3/placebo IMP prior to surgery.

Patients who require analgesia or antipyretic treatment during the course of the trial will be advised to use paracetamol rather than aspirin, ibuprofen or other NSAIDs. Any additional use of aspirin or NSAID

should be avoided, and where unavoidable, should be recorded on the patient diary card provided, and the Concomitant Medications eCRF

Administration of IMP will be discontinued in the following circumstances:

- Development of hypercalcaemia confirmed by blood sample
- Development of new dyspepsia symptoms or gastro-intestinal bleeding
- Development of a condition which requires treatment with a prohibited concomitant therapy
- Development of a condition which, in the judgement of the investigator, adversely affects the participant's safety, compliance or ability to complete evaluations
- If the investigator concludes that this course of action is in the participant's best interests

Should a patient become concerned that a symptom is potentially related to a study medication, it would be preferable to consider a dose interruption e.g. an alternate daily dose, or offer a 'treatment holiday', rather than stop treatment completely. Dose interruptions can be up to 30 days in the case of suspected toxicity. Longer 'treatment holidays' must be discussed with the PROVENT CCO. However, patients who interrupt study drug intake for a cumulative total of greater than 60 days, in a 3 month period between follow-up appointments, will be considered as non-compliant and will be discontinued from the study. An 'End of Study, eCRF will be completed

'Treatment holidays' can also be used in other special circumstances, at the discretion of the PI, but any dose interruptions of greater than two weeks, for reasons other than toxicity must be discussed with the PROVENT CCO. All variations in dose regime/daily dose, must be documented on the relevant eCRF, & in the patient diary.

Full treatment may be restarted after an appropriate interval, (no longer than 60 days), if symptoms have resolved, or a decision may then be made about withdrawal, if symptoms persist. Any variation in dose regime should always be documented on the relevant Case Report Form and in the patient diary.

Participants who discontinue the study drugs for any reason will not be considered to have left the study, and will be followed up for primary and secondary outcome measures. These patients will be included in the intention to treat and safety analyses.

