Patients may withdraw from the trial at any time at their own request or they may be withdrawn at any time at the discretion of the investigator if it is considered to be in the best interest of the patient. Patients can withdraw without giving a reason, but if a reason is given this should be documented in the eCRF and medical notes. It is possible for a patient to withdraw from treatment but continue to be followed up via eCRF, in clinic or by telephone. A 'Withdrawal from Treatment' eCRF will be completed. If patients do not wish to continue in this way, an 'End of Study' eCRF will be completed and they will not have any further visits.

The main analyses will be by intention to treat, therefore, data and samples collected up to the time of withdrawal of consent will be included in the study analyses, as stated in the consent form. Such data or samples will be included in the analysis, unless explicitly forbidden, again, in writing by the participant.

Patients may be withdrawn from trial medication, and/or the study in the event of:

- Unacceptable toxicity/intolerable side effects
- Inter-current illness
- Patient withdrawing consent
- Patient unable to comply with the study schedule
- Interruption of study drug intake for greater than 60 days
- Patient chooses to come off Active Surveillance and undergo active therapy
- Rise in serum calcium above upper limit of normal or 2.65mmol/l
- Identification of higher risk disease unsuitable for surveillance following 'For Cause' repeat prostate biopsy precipitated by an increasing PSA
- Development of new dyspeptic symptoms, or any sign of gastro-intestinal bleeding (haematemesis, melaena, decreased haemoglobin)
- Any episode of haemorrhage or development of a bleeding disorder
- Development of a condition not compatible with the study, or the addition of a new incompatible medication e.g. NSAID, or other product as in section 4.10
- Disease progression

Data concerning toxicity will be collected using the diary cards issued to all participants, which will allow symptoms to be classified as mild, moderate or severe. Data will also be collected on the Case Report Forms regarding gastro-intestinal bleeding and hypercalcaemia. Blood calcium levels will be monitored six monthly and any emergency hospital admissions reported, in which hypercalcaemia is identified, will be documented and followed up by the research team.

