Patients who interrupt study drug intake for a cumulative total of greater than 60 days, in a 3 month period between follow-up appointments, will be considered as non-compliant and will be discontinued from the study. An 'End of Study, eCRF will be completed, and no further follow-up appointments conducted. These patients will be included in the intention to treat and safety analyses. They will be included in the efficacy assessment only if they have received at least three 90 day cycles of treatment.

Patients will be considered to be lost to follow-up if there has been as no contact for ≥6 months from the last scheduled clinic visit. These patients will be included in the intention to treat and safety analyses. They will be included in the efficacy assessment only if they have received at least three 90 day cycles of treatment.

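### Protocol section 4.11 gives two conflicting study statuses to a man with new dyspepsia or GI bleeding: withdrawn from the study, or still in it and followed up

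*Protocol*

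**What the plan says.** Protocol section 4.11 deals with new dyspeptic symptoms and gastro-intestinal bleeding twice.

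- In its second paragraph: "treatment with aspirin/aspirin placebo should cease immediately and permanently, and the patient will withdraw from the study".
- Further down, among the circumstances in which study medication is discontinued: "Development of new dyspepsia symptoms or gastro-intestinal bleeding". The section then closes with: "Participants who discontinue the study drugs for any reason will not be considered to have left the study, and will be followed up". That last sentence goes on to name the primary and secondary outcomes as the purpose of follow-up, and places these men in the intention-to-treat and safety analyses.

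Three other sections bear on the same man.

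- Section 3.4 lists the same event under "Patients may be withdrawn from trial medication, and/or the study in the event of", which is permissive. It also separates two statuses. A man may stop treatment and still be followed, with a Withdrawal from Treatment form. If he does not want that, an End of Study "eCRF will be completed and they will not have any further visits".
- Section 4.5 says that men who cannot tolerate the medication will be withdrawn from the study.
- Section 5.12 keeps withdrawn subjects under three-monthly clinic follow-up for the rest of the trial, except those who withdraw permission in writing. Its stated reason is that the main analyses are by intention to treat.

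**The concern.** One event leads to two incompatible instructions inside one section. A site that acts on the first can treat the man as having left the study, while a site that acts on the last keeps him in.

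What is at stake is outcome data. The secondary endpoints rest on PSA, MRI and biopsy at 12 months. The trigger is broad, since dyspepsia of any severity counts, and section 1.2 itself names gastro-intestinal bleeding as a known effect of aspirin. Men lost by this route are therefore plausibly not a random subset: the loss may be more frequent on aspirin than on placebo. Such missingness undermines an intention-to-treat comparison, and an analysis plan cannot recover data that sites were told not to collect.

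There is also a smaller feasibility cost. Section 8.3 asks the Data Monitoring Committee to track drop-out, and the same man is a drop-out under one sentence and not under the other.

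**Working it through.** No formula applies to the contradiction, so the check sets the texts side by side.

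| Place in the Protocol | Medication | Study status | Follow-up |
|---|---|---|---|
| 4.11, second paragraph | Aspirin/placebo stops permanently | Withdraws from the study | Not stated |
| 4.11, discontinuation list and closing paragraph | Study medication discontinued | Has not left the study | Continues |
| 3.4, list of withdrawal events | May be withdrawn | May be withdrawn | Depends on which form is used |
| 4.5, men unable to tolerate medication | Implied stop | Withdrawn from the study | Not stated |
| 5.12 | Not stated | Withdrawn | Three-monthly, unless permission is withdrawn in writing |

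1. **Is it the same event?** Yes. The second paragraph and the later list of 4.11 both name new dyspepsia and gastro-intestinal bleeding. The closing paragraph covers any reason for stopping and makes no exception.

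2. **Could withdrawal from the study be loose wording for stopping tablets?** Not safely. The sentence has already stopped the tablets and adds study withdrawal as a second consequence. Section 3.4 treats the two statuses as different and gives each its own form.

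3. **Does section 5.12 resolve it?** Only in part. It shows that retention is intended and softens the practical effect. It does not say which status the man has or which form the site should file.

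4. **What is lost if an End of Study form is filed?** In the section 5.5 schedule, a man withdrawn before month 18 has MRI and biopsy recorded only if they happened to be done. PSA appears once, at withdrawal. The final End of Study column carries adverse events only.

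5. **How many men?** This cannot be computed, because the protocol gives no rate of new dyspepsia or bleeding. The weight of each loss can be. Section 3.1 plans 17 men per arm, so 4 × 17 = 68 men on active aspirin and 2 × 17 = 34 on aspirin placebo, with 34 at each aspirin dose. One man lost is 1/34 = 2.9% of a dose group, or 1/17 = 5.9% of a single arm.

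**The case against.** The best defence is that the second paragraph of 4.11 does not itself end follow-up. It mentions neither an End of Study form nor an end to visits, whereas the rules that do end follow-up (radical therapy and non-compliance in section 3.4) say so outright. Read with section 5.12, both sentences lead to continued follow-up. In addition, 12-month MRI and biopsy are routine care on surveillance (sections 5.4 and 5.8), PSA is standard practice (section 5.5 key), and this is a feasibility study whose primary endpoint is recruitment. All of this stands as a limit on the size of the problem. It does not make the two statements of study status compatible, and routine-care results still have to be recorded for the study.

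A reader might infer more than the text supports, in four ways.

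- *That any End of Study form ends visits for these men automatically.* In section 3.4 that consequence is tied to men who do not wish to continue in follow-up.
- *That the 60-day non-compliance rule, with its "eCRF will be completed, and no further follow-up appointments conducted", removes nearly all of them.* That rule concerns men who interrupt intake and are judged non-compliant. A permanent stop ordered by the protocol is not naturally an interruption, and the second paragraph of 4.11 stops only aspirin/placebo, not the oil.
- *That men stopped early drop out of the efficacy assessment under the three-cycle condition in section 3.4.* For these men, that rests on the same strained reading.
- *That tablets might be continued or restarted*, because 4.11 says "it would be preferable to consider a dose interruption e.g. an alternate daily dose" and "Full treatment may be restarted after an appropriate interval, (no longer than 60 days), if symptoms have resolved". Those are general provisions for a patient's worry about a symptom. The specific instruction to stop immediately and permanently governs.

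**Conclusion.** The contradiction is established from the wording alone: one section, one trigger, two incompatible study statuses, with a parallel problem in section 4.5. It concerns status and follow-up, not continued exposure, since every passage that mandates action stops aspirin/placebo.

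The consequence is conditional. If sites follow the second paragraph of 4.11 and file an End of Study form, 12-month MRI, biopsy and PSA data may be lost in a way plausibly related to aspirin. This assumes that some sites would read the sentence that way, and that dyspepsia and bleeding are more frequent on aspirin. The second assumption fits the protocol's own account of aspirin but is not quantified there. The number of men affected is unknown, part of the data exists in routine care, and the recruitment endpoint is not affected. The documents do not support putting a time or a count on the loss.

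**What to change.** - **Section 4.11, second paragraph.** Replace the final clause on leaving the study with: *and the patient will be withdrawn from aspirin/placebo treatment (Withdrawal from Treatment eCRF) but remain in scheduled follow-up unless he declines or the investigator judges that follow-up is not in his best interest.* This preserves the investigator's discretion in sections 3.4 and 5.11.
- **Section 4.5.** Make the same change for men who cannot tolerate the medication. Otherwise the conflict survives there.
- **Sections 3.4 and 4.11, as a clarification.** State that a permanent stop mandated by the protocol is not an interruption under the 60-day non-compliance rule.

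Whether the oil continues after an aspirin stop is for the sponsor to decide.

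The cost is a few words at the next amendment and a note to sites. No visits or procedures are added, because the men stay on visits already scheduled.

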3.0 Subject Selection

3.1 Number of Subjects and Subject Selection

This feasibility study aims to randomise 102 men within a period of twelve months. The study population is male patients over 16 years of age, who have been diagnosed with prostate cancer, have an estimated life expectancy of more than three years, and who have opted for Active Surveillance as their preferred prostate cancer therapy.

Participants must fulfil the inclusion and exclusion criteria. All patients who meet the eligibility criteria and are randomised will be included in the intention to treat (ITT) analysis.

17 men will be randomised into each of the six study arms in a 3 x 2 factorial design with a 1:1:1:1:1 ratio. In order to maintain treatment blinding, placebo aspirin will be size matched with the active treatment, and given as either a small (100mg) size or standard (300mg) size.

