3.4 Criteria for treatment discontinuation and early withdrawal

Treatment discontinuation

One year following study entry, patients will undergo disease reclassification to identify cancers that have progressed over the 12-month period. Disease reclassification will include repeat MRI of the prostate, together with repeat systematic and targeted prostate biopsy. Any patient whose cancer has progressed as defined in section 1.1, may continue on the study, providing they;

- are still deemed suitable for continued surveillance by their treating clinician
- do not undergo radical therapy &
- are authorised to do so by the Principal Investigator at that centre.

The reason for continuing on Active surveillance should be documented on the eCRF.

Patients undergoing radical therapy will discontinue study medication and an End of Study eCRF will be completed. No more study follow-up appointments will take place. The decision to proceed with radical therapy will be at the clinician's and patient's discretion. Unless explicitly requested in writing, by the

participant, data collected up to the 'End of Study' date will remain part of the trial. This will usually include the 12mth samples & eCRFs, as in most cases, these will have already been collected by the time the results of the disease reclassification are available.

Where a radical prostatectomy is carried out, every effort will be made to obtain pathological data and/or tissue, providing it can be acquired before the participant attends their PROVENT End of Study appointment. It is estimated that up to 30% of men will be identified to have disease progression upon disease reclassification.

Where progression is found and/or the decision is made to undergo radical therapy after 12 months but before 18 months, the participant will be required to leave the trial. An End of Study form must be completed, \geq 30 days after the participant took their last dose of IMP, for post treatment pharmacovigilance. Samples that would normally have been obtained at the 18 month follow-up appointment, will be collected wherever possible.

Early withdrawal

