5.12 Data Collection and Follow Up for Withdrawn Subjects

Data collected up to the time of withdrawal of consent will be included in the study analyses, as stated in the consent form, unless participants specifically withdraw permission to do so in writing. With the exception of such patients, withdrawn subjects will remain under three monthly follow-up in clinic for the duration of the trial, as the main analyses will be by intention to treat.

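### Section 4.11 makes staying on the study, rather than staying on aspirin, depend on completing H. pylori treatment, which is inconsistent with the protocol's own follow-up rules

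*Protocol*

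**What the plan says.** Under sections 5.2 and 5.4 the stool specimen is brought to the randomisation appointment. Section 4.11 lets the man start his tablets before the result is known. A positive result removes no one: he is sent to his GP for a 7-day course (section 5.2) and keeps taking study drug meanwhile. The condition is that he completes the course: "They will not need to stop the study medication, but may not continue on the study without completing the H Pylori treatment". Sections 5.2 and 5.4 likewise make treatment a condition of continuing in the study. Section 4.11 gives the purpose as lowering any added risk of gastric bleeding.

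Other parts of the protocol separate stopping drug from leaving the trial:

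- End of section 4.11: "Participants who discontinue the study drugs for any reason will not be considered to have left the study". These men are followed for primary and secondary outcomes and stay in the intention-to-treat and safety analyses.
- Section 3.4: "It is possible for a patient to withdraw from treatment but continue to be followed up via eCRF, in clinic or by telephone".
- Section 5.12, giving intention to treat as the reason: "withdrawn subjects will remain under three monthly follow-up in clinic for the duration of the trial". The exception is men who withdraw permission in writing.
- Section 3.1: "All patients who meet the eligibility criteria and are randomised will be included in the intention to treat (ITT) analysis".

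**The concern.** The condition takes effect after randomisation, so a man who fails it already belongs to the intention-to-treat set. If he goes, the result is missing outcome data and not a screening failure. The sentence names both the drug and the study, and attaches the consequence to the study. A site could reasonably complete an End of Study form and stop his visits. Another site, relying on the end of section 4.11 or on section 5.12, would keep him in follow-up. With up to seven centres, the same man could be handled in two ways.

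What is at stake is the information due after his exit: three-monthly PSA, the 12-month MRI and biopsy, and adverse events. The withdrawal visit in section 5.5 would capture some data as he leaves, but not what comes later. The bleeding concern is about aspirin, and stopping the tablets would meet it without ending follow-up.

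**Working it through.** **1. The plan's own figure.** Section 8.4 gives 89% power with 300 men approached, a true recruitment rate of 33.3% against 25%, and a two-sided 0.05 level.

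- Normal approximation: z = [(1/3 − 0.25) − 1.96 × √(0.25 × 0.75/300)] / √((1/3)(2/3)/300) = (0.0833 − 0.0490)/0.0272 = 1.26, so power is 89.6%.
- Exact binomial: reject at 91 or more of 300 (upper-tail probability 0.0210 under 25%), power 87.8%.

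The figure reproduces. It concerns who joins the trial, so events after randomisation cannot change it.

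**2. The texts side by side.**

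| Situation | Status | Follow-up |
|---|---|---|
| H. pylori course not completed (4.11) | may not continue on the study | not stated |
| Study drug discontinued, any reason (end of 4.11) | has not left the study | continues |
| Withdrawn subject (5.12) | withdrawn | three-monthly, for the trial's duration |
| Radical therapy (3.4) | End of Study form | "No more study follow-up appointments will take place" |
| Over 60 days' interruption (3.4) | discontinued from the study | "eCRF will be completed, and no further follow-up appointments conducted" |

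Where the protocol means visits to stop, section 3.4 says so. The H. pylori sentence does not. It can be read as exit (A) or as withdrawal with follow-up under section 5.12 (B). Nothing in the paragraph points the site to the rule at the end of the section.

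**3. Size, on assumed rates.** The protocol gives neither rate. Purely to show scale, assume 5% to 40% positive and 10% to 30% of those not completing.

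- Low: 102 × 0.05 × 0.10 = 0.5 men.
- Middle: 102 × 0.20 × 0.20 = 4.1 men.
- High: 102 × 0.40 × 0.30 = 12.2 men, or 12.2/6 = 2.0 per arm of 17.

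Under reading B nothing is lost. Under reading A, if every such man left before month 3 with no later results, the standard error of a whole-cohort proportion would rise by a factor between √(102/101.49) = 1.003 and √(102/89.76) = 1.066. The upper figure needs the highest assumed rates, reading A at every site and the earliest exit, all together.

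**The case against.** The strongest reply is that the protocol already answers the question. The closing rule of section 4.11 covers discontinuation for any reason and makes follow-up mandatory. The same section lets the investigator stop study drug in the man's best interests. Sections 3.4 and 5.12 point the same way. A reader might infer that section 4.11 offers no way to stop aspirin and remain in follow-up. That is not so, because the section itself supplies one.

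This narrows the point without removing it. The closing rule applies to men who have discontinued drug, whereas the H. pylori sentence says they need not stop it and then says they may not stay on the study. Uncompleted treatment is not a named reason for stopping drug. It could enter only through the investigator-judgement items. Section 3.4 makes treatment-only withdrawal possible but does not direct it here.

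A reader might also infer that the 60-day rule would soon end follow-up for a man who stops his tablets. That rule concerns "patients who interrupt study drug intake for a cumulative total of greater than 60 days, in a 3 month period between follow-up appointments", and it stands beside the text on treatment holidays and restarting. A permanent stop is naturally a discontinuation, to which the closing rule applies.

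Two further objections are fair. Section 4.11 has firmer wording on the same issue in its dyspepsia and bleeding paragraph, where the man is to withdraw from the study. And continuing Vitamin D3/placebo alone is not a trivial edit: section 4.6 describes a pack holding both products, and section 4.9 says the pack components should not be separated.

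**Conclusion.** The point holds as an internal inconsistency of minor importance. The H. pylori sentence reads as study exit, while the end of section 4.11 and section 5.12 keep such a man in follow-up. It is not a flat contradiction, since the sentence does not say that visits stop.

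The loss arises only at sites that adopt the exit reading. It is then confined to secondary outcomes and safety data after exit. Under section 3.4, data up to withdrawal are kept unless the man forbids it in writing, and he stays in the intention-to-treat set. The number of men cannot be estimated from the protocol. The range of 0.5 to 12 of 102 rests wholly on assumed rates and should not be taken as an expected loss. Recruitment and the 89% power are untouched.

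**What to change.** In section 4.11, replace the quoted sentence with wording such as:

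> A participant who does not complete H. pylori treatment will permanently discontinue aspirin/placebo but will remain in scheduled follow-up and in the ITT and safety analyses, as for any participant who discontinues study drug (end of section 4.11, section 5.12).

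Align the matching conditions in sections 5.2 and 5.4. Whether Vitamin D3/placebo continues is for the sponsor to decide, given the combined packs. The 60-day rule needs no separate change, provided the stop is recorded as a discontinuation.

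The cost is a few sentences. No visit or test is added: section 5.4 schedules follow-up alongside routine Active Surveillance appointments and treats the 12-month MRI and biopsy as routine care. The downside is a few more men off aspirin in the intention-to-treat comparison.
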